The PRO assessments will be completed by all subjects at sites where appropriate PROs and translations are available and approved. Subjects should complete the PRO assessments in a language in which the subject is fluent and literate. Study personnel will instruct subjects how to self-complete the PRO assessment. Incapacitated subjects and subjects who develop a decreased level of consciousness or are intubated will not complete PROs.

Site personnel can enter responses on the ePRO device on behalf of subjects only when subjects are too ill to hold devices in their hands but are able to respond to questions. If these criteria are met, site personnel will log into the ePRO device under the Site ID module, will read the instructions, questions, and potential responses aloud and in entirety to subjects, and enter their responses into the ePRO device. If the subjects cannot provide verbal responses, site personnel should document that the reason for missing data is due to illness. Site personnel will not allow caregivers or family members of subjects to complete the PROs. Site staff will complete specific training on these study procedures.

Subjects will complete the PRO assessments electronically on a touch screen computer (ePRO device) provided for this study. The subject should be provided a quiet place to complete the PRO assessments. When deciding which answer to report, subjects should not be influenced by anyone accompanying them (such as family members and friends) or study personnel; the responses should reflect the subject's interpretation and response.

Subjects' responses to the PRO questionnaires will not be reported as AEs or SAEs.

PRO completion compliance should be assessed daily by the site staff via the ePRO web platform. Reasons for missing assessments should be documented on the web platform by the site after discussion with the subject.

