- If the p-value for “Incidence in post-baseline complications” is $\leq 2.5\%$ but the p-value for “Time from start of study drug to hospital discharge” is $> 5\%$, stop further testing of the secondary endpoints, and make a claim on “Hospital recovery scale at Day 6” and “Incidence in post-baseline complications”.
- If the p-value for “Time from start of study drug to hospital discharge” is $\leq 2.5\%$ but the p-value for “Incidence in post-baseline complications” is $> 5\%$, stop further testing of the secondary endpoints, and make a claim on “Hospital recovery scale at Day 6” and “Time from start of study drug to hospital discharge”.
- If the smallest of the 2 p-values is $> 2.5\%$, stop further testing of the secondary endpoints, and make a claim on “Hospital recovery scale at Day 6” only.

Step 3: Test second set of 2 secondary endpoints (“Time from ICU admission to ICU discharge” and “Time to return to daily activities”). The Bonferroni-Holm procedure will be applied within Step 3.

- If the smallest of the 2 p-values is $\leq 2.5\%$ and the largest of the 2 p-values is $\leq 5\%$, continue to Step 4.
- If the p-value for “Time from ICU admission to ICU discharge” is $\leq 2.5\%$ but the p-value for “Time to return to daily activities” is $> 5\%$, stop further testing of the secondary endpoints, and make a claim on “Hospital recovery scale at Day 6”, “Incidence in post-baseline complications”, “Time from start of study drug to hospital discharge” and “Time from ICU admission to ICU discharge”.
- If the p-value for “Time to return to daily activities” is $\leq 2.5\%$ but the p-value for “Time from ICU admission to ICU discharge” is $> 5\%$, stop further testing of the secondary endpoints, and make a claim on “Hospital recovery scale at Day 6”, “Incidence in post-baseline complications”, “Time from start of study drug to hospital discharge” and “Time to return to daily activities”.
- If the smallest of the 2 p-values is $> 2.5\%$, stop further testing of the secondary endpoints, and make a claim on “Hospital recovery scale at Day 6”, “Incidence in post-baseline complications” and “Time from start of study drug to hospital discharge”.

Step 4: Test the fifth secondary endpoint (“Time from start to end of mechanical ventilation”)

- If the p-value is $\leq 5\%$, continue to Step 6.

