- If the p-value is $> 5\%$, stop further testing of the secondary endpoints, and make a claim on “Hospital recovery scale at Day 6”, “Incidence in post-baseline complications”, “Time from start of study drug to hospital discharge”, “Time from ICU admission to ICU discharge”, and “Time to return to daily activities”.

Step 5: Test the sixth secondary endpoint (“Rate of re-hospitalization”)

- If the p-value is $\leq 5\%$, make a claim on “Hospital recovery scale at Day 6”, “Incidence in post-baseline complications”, “Time from start of study drug to hospital discharge”, “Time

from ICU admission to ICU discharge”, “Time to return to daily activities”, “Time from start to end of mechanical ventilation”, and “Rate of re-hospitalization”.

- If the p-value is >5%, make a claim on “Hospital recovery scale at Day 6”, “Incidence in post-baseline complications”, “Time from start of study drug to hospital discharge”, “Time from ICU admission to ICU discharge”, “Time to return to daily activities”, and “Time from start to end of mechanical ventilation”.

For the primary endpoint, the results from the proportional odds model will be used in the hypothesis testing. If the proportional odds assumption would not hold on the treatment effect, the p-value from the van Elteren test will be used. For the secondary endpoints time from start of study drug to hospital discharge, time from ICU admission to ICU discharge, time to return to daily activities, and time from start to end of mechanical ventilation, the results of the Gehan-Wilcoxon test will be used in the hypothesis testing. For incidence in post-baseline complications and rate of re-hospitalization the results of the logistic regression will be used. For all these evaluations p-value combination tests will be used, as described below.

The final analysis on the ITT-i set (to support FDA marketing approval) and the final analysis on the OST subset (to support marketing authorization approval in EMA) will be performed independently, using a 5% two-sided significance level for each.

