5.3. Major Secondary Endpoints

5.3.1. Definition

Formulae to be used for derived variables, including data conversions, are provided in the tables below.

Note that for time-to event variables the actual date or times that the endpoint is met will be used. For the time-to-event variables, in case of death prior to the event, the subject will be censored using a time-to equal to the maximum time across all subjects.

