5.3.1.3. Patient Reported Outcomes

Measurement	Formula
Daily activities resumption	
The daily activities resumption will be assessed once daily by means of the question 'Over the past 24 hours, how much has influenza interfered with your ability to carry out your daily activities?'
 
The responses will be dichotomized: 'Not at all' and 'A little bit' will be considered as category “returned to daily activities” and responses 'Somewhat', 'Quite a Bit' and 'Very much' will be considered in category “not returned to daily activities”.

Time to return to daily activities (days) [Time-to event]	
The time to return to daily activities is defined as the time in days from initiation of study treatment (baseline assessment excluded) to the first of a successive series of 2 recordings in which the response is considered as returned to daily activities. The 2 successive recordings may have been done over 3 scheduled successive analysis timepoints, in case of 1 missing in between timepoint.
 
In case the return to daily activities is not achieved, data will be censored.
 
Censoring will be done as follows:
 
 1) Last non-missing record in indicate return to daily activities (but insufficient recordings) Censoring will be done at the first record of return to daily activities 2) Last non-missing record does not indicate return to daily activities Censoring will be done one day (24 hours) after the last observation. 
The time to return to daily activities is calculated as: Date and time of event (actual) or censoring - date and time of first dose of study drug)/(3600*24), rounded to one decimal.
 
Subjects without postbaseline records are excluded from the analysis.

Patient Global Impression of Severity of Influenza symptoms	
The PGIS captures daily influenza symptom severity from the subjects’ perspective per timepoint. Responses will be categorized as :“No Flu symptoms today”, and “Mild”, "Moderate", "Severe" or “Very Severe”.

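### Time to return to daily activities: survivors whose diary stops for good because of intubation, incapacity or reduced consciousness are censored a day after their last entry, and those with no post-baseline entry are excluded

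*SAP*

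**What the plan says.** - **Who completes the diary.** Protocol 9.2.1.3: "Incapacitated subjects and subjects who develop a decreased level of consciousness or are intubated will not complete PROs". The same section has site staff document illness as the reason when a subject cannot answer verbally.
- **Censoring.** SAP 5.3.1.3 distinguishes two cases without a confirmed return. The relevant one is headed "Last non-missing record does not indicate return to daily activities", and its rule is "Censoring will be done one day (24 hours) after the last observation". The reason the diary stopped is not used.
- **No diary at all.** SAP 5.3.1.3: "Subjects without postbaseline records are excluded from the analysis".
- **Death.** SAP 5.3.1 sets a general rule that covers this endpoint too: "in case of death prior to the event, the subject will be censored using a time-to equal to the maximum time across all subjects".
- **Role of the endpoint.** In SAP 5.1.1 it is tested in Step 3, in a Bonferroni-Holm pair with time from ICU admission to ICU discharge. For the time-to-event endpoints in the sequence, "the results of the Gehan-Wilcoxon test will be used in the hypothesis testing". If either member of the pair fails, endpoints 6 and 7 are not tested.
- **Sensitivity analysis.** Multiple imputation is specified only for the Day 6 hospital recovery scale (SAP 5.2.2 and 5.2.3). Nothing comparable is given for this endpoint.

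**The concern.** The censoring rule treats a silent diary as carrying no information. For one group the protocol itself makes silence a marker of a bad course: subjects who deteriorate to intubation or reduced consciousness, survive, and do not take the diary up again. They had not returned to daily activities, and ventilation dates and consciousness scores can show this for days after the last entry. Censoring them at that entry lets the remaining, healthier subjects stand in for them.

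If pimodivir changes the frequency of such deterioration, the affected share differs between arms and part of that difference drops out of the comparison, whichever way it goes. The Gehan-Wilcoxon test gives most weight to early times, which is where early stoppers would be lost. Excluding subjects with no post-baseline entry is a separate selection after randomization, and it also falls on very ill subjects, because ventilated subjects are eligible (Protocol 4.1, criterion 5).

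**Working it through.** **1. What the rules do to each course.**

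| Course | Handling | Affected? |
|---|---|---|
| Deteriorates, dies before return | Censored at the maximum time across subjects (SAP 5.3.1) | No |
| Intubated, recovers, resumes diary | The rule keys on the last record overall, so the subject stays at risk | No |
| At least one post-baseline entry, stops through illness, survives, never resumes | Censored 24 h after the last entry | Yes |
| Too ill for any post-baseline entry, survives | Excluded | Yes |

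Example: last entry on Day 4 showing no return, intubated, alive at Day 28, no further entries. The subject is censored on Day 5. For time to hospital discharge (SAP 5.3.1.1) the same subject, if still hospitalized, stays at risk until completion or withdrawal.

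**2. How many.** No figure is given. The nearest is the planning assumption that 5% of placebo subjects are on invasive ventilation on Day 6 (SAP 1.4), which is 0.05 × 300 = 15 subjects. This is only a rough guide. It includes later deaths, subjects who recover and resume, and subjects with no post-baseline diary; it omits reduced consciousness without intubation.

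**3. The plan's own power figure.** The documents state power only for the primary endpoint. Whitehead's formula is N = 12(1.960 + 1.282)² / [ln(0.62)² × (1 − Σp̄³)], with placebo 30/30/25/5/5/5% and the shifted pimodivir distribution 40.9/29.9/19.4/3.4/3.3/3.2%. It gives N = 601.4, and 89.9% power at 600, so the stated 600 and 90% reproduce. The present point does not bear on that figure, and there is no corresponding figure for this endpoint.

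**4. Model A: no treatment effect on return among the others.** Assumptions: 300 per arm, exponential return times with median 10 days, follow-up to Day 28, last entry on Day 1 to 5 in the affected share, who survive and never resume; unstratified Gehan-Wilcoxon test, 1,000 replicates. The comparator keeps affected subjects at risk, not returned, to Day 28. Positive Z favours pimodivir.

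| Share affected, pimodivir / placebo | Mean Z, SAP rule | Mean Z, kept to Day 28 | Chance Z > 1.96, SAP rule | Same, kept to Day 28 |
|---|---|---|---|---|
| 5% / 5% | 0.03 | 0.03 | 2.6% | 3.0% |
| 3% / 5% | 0.05 | 0.30 | 2.5% | 4.7% |
| 5% / 10% | 0.23 | 0.87 | 3.6% | 13.0% |
| 10% / 5% | −0.26 | −0.91 | 1.7% | 0.5% |

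At 5% in both arms, the Kaplan-Meier proportion returned by Day 14 is about 0.615 under the SAP rule and 0.590 with these subjects kept at risk. The estimate is 2.5 points too favourable in each arm while the test hardly moves. At 5% against 10%, most of the between-arm signal is lost, in either direction.

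**5. Model B: benefit among the others.** Assumptions: log-normal return times, sigma 0.7, placebo median 9 days, time ratio 0.85, deterioration uniform over days 1 to 5; 2,000 replicates. The third column of results holds subjects at risk only while the documented state lasts (assumed median 7 days, log-normal sigma 0.6). Entries are the chance of a significant result favouring pimodivir.

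| Share affected, placebo / pimodivir | SAP rule | Kept to Day 28 | Kept while state lasts |
|---|---|---|---|
| 5% / 3% | 80% | 85% | 83% |
| 1% / 2% | 78% | 70% | 75% |
| 3% / 5% | 74% | 56% | 66% |
| 5% / 8% | 74% | 47% | 60% |

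In the last two rows the state-limited rule delivers (74 − 66)/(74 − 56) = 8/18 and (74 − 60)/(74 − 47) = 14/27 of the Day 28 change, about half. With no effect and 5% affected in both arms, the chance is 2.1% under the SAP rule and 2.4% under the state-limited rule.

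Neither model includes the subjects excluded for want of a post-baseline entry.

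**The case against.** The strongest case against is one of scope. Deaths are already held to the maximum time, resumers stay at risk, and what remains may be few: no document supports shares of 3% to 10% per arm. Deterioration is also captured elsewhere, in the primary scale, post-baseline ICU admission, post-baseline ventilation and time to clinical failure. All of this stands, and it limits the size of the problem. It does not supply a rule for the survivors who are affected.

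Four stronger readings are tempting, and the documents do not support them.

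- *The worst courses leave the risk set.* The worst course is death, which SAP 5.3.1 retains. The point concerns surviving never-resumers and those excluded.
- *The rule hides a harm.* It can mute one on this endpoint; the outcomes listed above would still show it.
- *The rule inflates false positives.* With equal shares and no effect the simulations show no inflation.
- *The simulated percentages are the trial's chance of a claim.* They describe one ungated, unstratified test. A claim also needs the Day 6 scale, complications and discharge to succeed first, then Holm within the pair (SAP 5.1.1), with p-values combined across the interim (SAP 5.1.2).

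There is also a fair objection to an over-broad remedy. ICU stay and non-invasive ventilation do not bar diary completion, and site staff may enter answers for subjects too ill to hold the device. Counting every such day as not returned would overwrite valid self-report. ACVPU is scheduled three times daily only to discharge or Day 14 (Day 19 with extended treatment), plus the final visit (Protocol 9.6.4 and the schedules), so it cannot carry the rule alone.

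**Conclusion.** The point holds in a limited form. For survivors whose diary stops for good because of intubation, incapacity or reduced consciousness, censoring 24 h after the last entry is informative. Excluding those with no post-baseline entry for the same reasons is informative selection. No other rule or sensitivity analysis in the SAP covers either group, although deaths are handled deliberately and time to discharge keeps comparable survivors at risk.

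The size is unknown because the affected share is not documented. With equal shares the effect on the test is negligible and the estimated return is modestly too high. With unequal shares a between-arm difference in deterioration is attenuated, and the direction depends on which arm deteriorates more. The simulated changes rest on assumed shares and assumed return-time distributions. The Day 28 comparisons are upper-bound illustrations, since a subject may recover without resuming the diary. This is a cheap improvement to an alpha-controlled endpoint, not a threat to the primary analysis.

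**What to change.** Before unblinding, amend SAP 5.3.1.3 as follows.

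1. A day **without** a diary entry counts as not returned if the subject is on invasive mechanical ventilation, has an ACVPU score other than Alert (where assessed), or has illness documented by the site as the reason for the missing entry.
2. Censor no earlier than the end of the last such day, or at study end if the state is ongoing. The existing rule for deaths is unchanged.
3. Never override an actual diary entry.
4. Include subjects with no post-baseline entry for these reasons on the same basis. Those without a diary for other reasons, such as no approved translation at the site, stay under the existing rule.
5. Add a sensitivity analysis that carries all illness-related diary stoppers as not returned to the end of follow-up.
6. Tabulate by arm the number censored or excluded for these reasons, so that the size of the problem becomes visible.

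The cost is SAP wording and a merge with data already collected: ventilation dates, ACVPU and the recorded reason for missing entries. The drawback is that for a few subjects the endpoint is no longer purely self-reported.

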5.3.2. Analysis Methods

Descriptive statistics

The descriptive statistics that will be shown may include the number of subjects, mean, standard deviation, standard error, 95% CI, median, range, interquartile range and geometric mean with corresponding 95% CI.

Kaplan-Meier analysis, Gehan-Wilcoxon test and Log-rank test

All Time-to event variables will be analyzed using a stratified Gehan-Wilcoxon test, a stratified log-rank test and Kaplan-Meier estimates. For endpoints where the start time is not the start of the treatment A summary table including number of subjects included in the analysis, number of subjects censored, 25th and 75th percentiles and median time-to event, with 95% confidence intervals based on log-log transformation method, and the p-values calculated based on the stratified Gehan-Wilcoxon test and stratified log-rank test will be presented.

The data will be presented graphically using the Kaplan-Meier estimate of the survival function by treatment.

For all subgroup analyses, Kaplan-Meier plots will be produced per subgroup and Gehan-Wilcoxon test will be produced for each category of a subgroup.

Accelerated failure time (AFT) model

When indicated, time-to event variables will be compared between pimodivir and placebo using an accelerated failure time (AFT) model. The distribution to be used will be determined based on the goodness of fit of the model using Akaike's information criterion and will be selected from the following parametric families: lognormal, log-logistic, or Weibull. The AFT model will include the fixed, categorical effects for treatment (with placebo as the reference), the time from admission to start of treatment (for the time to hospital discharge and time to hospital discharge readiness) and stratification factors (type of baseline SOC, time of onset of symptoms and screening NEWS2). The scale parameter will be the same across groups

A summary of the final AFT model will include parameter estimates and associated standard errors, estimated accelerated failure time ratios versus placebo and associated 95% confidence intervals, and p-values. The survival curves per treatment group of the accelerated failure time model will also be shown with the Kaplan-Meier plots included in the same output.

For subgroup analyses the survival curves will be shown for each subgroup category separately.

Bootstrapping with replacement, considering also the actual proportion of subjects in each stratum, will be used to obtain a 100% sample size 10001 times. The median (95% CI) time-to event will be derived from the 10001 bootstrapped samples.

Cox Proportional Hazard model

A stratified Cox proportional hazards model will be used adjusted for the stratification factors and for the time from admission to start of treatment (for the time to hospital discharge and time to hospital discharge readiness),. The hazard ratio for the comparison of pimodivir versus placebo will be reported together with the 95% confidence interval. A Log-log plot of survival will be added to check the proportional hazard assumption of the Cox proportional hazards model.

For the subgroup analyses the Log-Log plot of survival will be shown for each subgroup category separately.

Logistic regression model

A logistic regression model (Firth's penalized likelihood approach), with treatment group and stratification factors as fixed effects, will be used to analyze binary outcomes and to obtain the odds ratios (95% CI) for the comparison of pimodivir versus placebo.

